## 13.0 Study Timelines\*

13.1 Describe the anticipated duration needed to enroll all study subjects.

Response:

It is anticipated that recruitment for this study will take approximately 18 months. Recruitment will begin in Summer 2019, pending IRB approval.

*13.2 Describe the duration of an individual subject's participation in the study. Include length of study visits, and overall study follow-up time.*

Response:

An individual subject's participation in the study will take place over about 6 weeks.

*13.3 Describe the estimated duration for the investigators to complete this study (i.e. all data is collected and all analyses have been completed).*

Response:

The proposed study will take place over approximately 2 years.

## **14.0 Setting**

*14.1 Describe all facilities/sites where you will be conducting research procedures. Include a description of the security and privacy of the facilities (e.g. locked facility, limited access, privacy barriers). Facility, department, and type of room are relevant. Do not abbreviate facility names.*

*NOTE: Examples of acceptable response may be: "A classroom setting in the Department of Psychology equipped with a computer with relevant survey administration software," "The angiogram suite at Buffalo General Medical Center, a fully accredited tertiary care institution within New York State with badge access," or, "Community Center meeting hall."*

Response:

Research will be conducted in the Division of Behavioral Medicine Laboratory located in [name], or remotely using UB's secure VPN in accordance with laboratory emergency procedures. [name] is secured suite with multiple private rooms. For this study, all participant contact will be remote (online or phone), and study staff will utilize computer/phone stations within [name] for these contacts. The study team may receive some additional office space in Farber Hall over the next 1-2 years. If study staff are seated in these offices, participant contact could take place in these additional offices within Farber Hall. These locations would have the same security features as the [name] location (door able to be closed and locked to ensure security and a private space for speaking with participants, computers password-protected, files saved on secure server, etc.).

*14.2 For research conducted outside of UB and its affiliates, describe:*

- *Site-specific regulations or customs affecting the research*
- *Local scientific and ethical review structure*

*NOTE: This question is referring to UB affiliated research taking place outside UB, i.e. research conducted in the community, school-based research,*

*international research, etc. It is not referring to multi-site research. UB affiliated institutions include Kaleida Health, ECMC, and Roswell Park Cancer Institute.*

Response:

☒ N/A: This study is not conducted outside of UB or its affiliates.

## 15.0 Community-Based Participatory Research

15.1 *Describe involvement of the community in the design and conduct of the research.*

*NOTE: Community-Based Participatory Research (CBPR) is a collaborative approach to research that equitably involves all partners in the research process and recognizes the unique strengths that each brings. CBPR begins with a research topic of importance to the community, has the aim of combining knowledge with action and achieving social change to improve health outcomes and eliminate health disparities.*

Response:

☒ N/A: This study does not utilize CBPR.

15.2 *Describe the composition and involvement of a community advisory board.*

Response:

☒ N/A: This study does not have a community advisory board.

***Describe other resources available to conduct the research.***

*16.2 Describe the time and effort that the Principal Investigator and research staff will devote to conducting and completing the research.*

*NOTE: Examples include the percentage of Full Time Equivalents (FTE), hours per week. The question will elicit whether there are appropriate resources to conduct the research.*

Response:

It is planned for the PI to devote about 5-15% effort to this study while it is taking place, with more effort anticipated at the beginning and end of the project. It is expected that study staff and students will spend about 5-20 hours per week on this project, depending on their particular role.

*16.3 Describe the availability of medical or psychological resources that subjects might need as a result of anticipated consequences of the human research, if applicable.*

*NOTE: One example includes: on-call availability of a counselor or psychologist for a study that screens subjects for depression.*

Response:

We do not anticipate that subjects will need medical or psychological resources as a result of the study.

*16.4 Describe your process to ensure that all persons assisting with the research are adequately informed about the protocol, the research procedures, and their duties and functions.*

Response:

All personnel working on the project are required to complete the CITI training as required by the IRB. Additionally, all study staff will be trained on data collection procedures by senior team members (the PI, graduate students working on the project, and/or [name], a senior undergraduate student with substantial research experience). The PI will provide initial training and continued oversight when students assume any leadership roles on the study.

## **17.0 Other Approvals**

*17.1 Describe any approvals that will be obtained prior to commencing the research (e.g., school, external site, funding agency, laboratory, radiation safety, or biosafety).*

Response:

☒ N/A: This study does not require any other approvals.

## **18.0 Provisions to Protect the Privacy Interests of Subjects**

18.1 *Describe how you will protect subjects' privacy interests during the course of this research.*

*NOTE: Privacy refers to an individual's right to control access to him or herself. Privacy applies to the person. Confidentiality refers to how data collected about individuals for the research will be protected by the researcher from release. Confidentiality applies to the data.*

*Examples of appropriate responses include: "participant only meets with a study coordinator in a classroom setting where no one can overhear", or "the participant is reminded that they are free to refuse to answer any questions that they do not feel comfortable answering."*

Response:

The recruitment procedures described in this protocol make use of posted flyers web postings, and secure databases of interested potential participants – methods approved by previous IRB committees. With regards to public postings, participants may call the laboratory or complete the online screening questionnaire of their own free will, and thus are controlling access to their privacy.

Other participants will be recruited using secure databases of interested participants maintained by the Division of Behavioral Medicine, Independent Health, the Center for Translational Sciences Institute (CTSI) and I2B2. Potential participants have signed up for these databases of their own free will. All recruitment details will be kept confidential and private. During the initial phone or online screening, data will be collected in the secure laboratory environment and will be recorded within password-protected files, to which only select staff have access. All information will be treated in strict confidence to the extent provided by the law.

All study data will be stored on a secure password-protected server, UBBox, and/or external hard drive locked in a cabinet in a secure room ([name]). Only the PI and members of the research staff will have access to the data. Personally identifiable information will be stored separately from coded data. A file linking participant identities with participant ID numbers will be stored separately from these data sources and will be password-protected and accessible only by the PI and senior Child Health and Behavior Lab staff. Participants' identities will not be linked with any published results.

Participants will be told they have the right to refuse to answer any question that makes them uncomfortable and to stop participating in the study at any time should they so choose.

18.2 *Indicate how the research team is permitted to access any sources of information about the subjects.*

*NOTE: Examples of appropriate responses include: school permission for review of records, consent of the subject, HIPAA waiver. This question **does apply** to records reviews.*

Response:

Participants will indicate their consent after reviewing consent forms and having the chance to ask the study team any questions. A HIPAA authorization will be completed before the research team can access medical information about participants' diabetes status and/or diabetes risk status (See attachment: Consent and HIPAA form). Then, HIPAA forms will be used to collect information needed to access information about participants' diabetes status and/or diabetes risk status. Physicians will be contacted using their modality of choice; this may include phone, email, fax, or in-person communication.

## **19.0 Data Management and Analysis\***

*19.1 Describe the data analysis plan, including any statistical procedures. This section applies to both quantitative and qualitative analysis.*

Response:

Linear mixed models will be used to test effects of the interventions on total calories, carbohydrates, sugar (total sugar and/or added sugar), and nutritional quality of grocery purchases, with study group, time, and their interaction as factors. Primary comparisons will be between-groups comparisons of these variables at post-test. We will also examine whether these variables differ overall by study group and whether changes in these variables differ by study group. We will conduct each analysis once for the total cart and then again examining these variables relative to household size and for items that the respondent indicated they would be consuming. We will conduct parallel analyses with total dollars spent each week and with DASH diet scores as outcomes to examine effects on spending and intake. We will also explore whether effects differ for participants with prediabetes vs. diabetes and whether results change when adjusting for food purchases beyond the target stores. Finally, we will test for relationships between purchases (calories, carbohydrates, and sugar (total sugar and/or added sugar)) and intake (DASH diet scores). We will also explore whether results differ when considering shopping trips completed by the participant only (vs. all trips for the household).

*19.2 If applicable, provide a power analysis.*

*NOTE: This may not apply to certain types of studies, including chart/records reviews, survey studies, or observational studies. This question is asked to elicit whether the investigator has an adequate sample size to achieve the study objectives and justify a conclusion.*

Response:

To estimate the sample size needed for this study, effect sizes from the most similar existing study were used: a proof-of-principle study examining the effects of defaults, incentives, and education strategies on healthfulness of grocery purchases among undergraduate students (Coffino & Hormes, 2018, Obesity). Based on the observed differences in calories purchased at post-test between defaults and education control groups (Cohen's  $d=0.96$ ), 15 participants would be needed for the primary comparison in the present study, with  $\alpha=.05$  and  $\text{power}=.80$ . We repeated this analysis using the difference between controls and

the prior study's intermediary group (incentives; Cohen's  $d=0.44$ ) to conduct a more conservative sample size calculation, given our interest in detecting effects on purchasing between our intermediary group (*Online*) and the other groups. This calculation yielded a sample size of 54. We increased this to account for participants lost during the run-in period (i.e. failure to confirm diabetes diagnosis, failure to complete baseline procedures) as well as participants lost due to attrition, with a plan to enroll up to 100 participants.

*19.3 Describe any procedures that will be used for quality control of collected data.*

Response:

Some data will be entered directly by participants (online questionnaires). All other study data will be entered by trained staff: study staff will enter participant responses into online forms while phone screening/phone interviews are completed. Study staff will also enter information from receipts into NutritionistPro (e.g., nutrition information) and Microsoft Excel (e.g., dollars spent) for analysis of study aims. Entered data will be double entered and/or checked for quality control.

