### Data to be collected include:

- \*Confirmation of diabetes status or diabetes risk status (see attachments: Consent and HIPAA Form)
- \*Demographic questions collected at baseline (see attachment: Questionnaires)
- \*Changes in daily routine, perceived stress and loneliness questions at baseline (see attachment: Questionnaires)
- \*Calories, carbohydrates, sugar (total sugar and/or added sugar), and food groups each week of the 5-week shopping period, from receipts (see additional details below)
- \*Information on which purchased items will be consumed by the participant and information about foods acquired from other sources besides the target grocery store that week (administered after each shopping trip, see attachment: Phone interview)
- \*Dollars spent on groceries at each time point, from receipts (each week)
- \*Dietary intake from a Food Frequency Questionnaire (see details below and attachment: Questionnaires; collected at post-test)
- \*Exit questionnaire (completed at the end of the study; see attachment: Questionnaires)

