### Additional details:

Calories, carbohydrates, sugar (total sugar and/or added sugar), and food groups will be generated from each of the five weeks of receipt data using Nutritionist Pro software. Each item on the receipt, as well as the item quantity and weight, will be entered into the software following procedures from Hollis-Hansen et al. (Hollis-Hansen, Seidman, O'Donnell, & Epstein, 2018). Standard values from the USDA will be entered in the case of any missing information as done previously. Nutritional quality will be examined using the DASH diet scores based on the amount of 8 food types encouraged or discouraged by the DASH diet (e.g., fruits,

vegetables, sweetened beverages). Methods previously used to calculate DASH diet scores from intake data will be adapted for use in this context.

The food frequency questionnaire is used to calculate nutrient intake. It is a structured self-administered questionnaire with pre-specified response options.

12.3 List any instruments or measurement tools used to collect data (e.g. questionnaire, interview guide, validated instrument, data collection form).

*Include copies of these documents with your submission.*

Response:

- Baseline demographic questionnaire – (see attachment: Questionnaires)
- Food frequency questionnaire (to be completed at post-test) – (see attachment: Questionnaires)
- Food receipt collection instructions (see attachment: Receipt collection)
- Food receipt form (see attachment: Receipt collection)
- Exit survey – (see attachment: Questionnaires)
- Consent and HIPAA form

12.4 Describe any source records that will be used to collect data about subjects (e.g. school records, electronic medical records).

Response:

N/A, no source records will be used to collect data about subjects.

12.5 Indicate whether or not **individual** subject results, such as results of investigational diagnostic tests, genetic tests, or incidental findings will be shared with subjects or others (e.g., the subject's primary care physician) and if so, describe how these will be shared.

Response:

N/A, no individual subject results will be shared with subjects or others.

12.6 Indicate whether or not **study** results will be shared with subjects or others, and if so, describe how these will be shared.

Response:

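### The primary post-test contrast is not adjusted for the baseline shopping week, which costs precision; the weeks behind the overall group effect also need defining

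*Combined protocol and SAP*

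**What the plan says.** Section 19.1 specifies linear mixed models for calories, carbohydrates, sugar and nutritional quality of purchases, "with study group, time, and their interaction as factors". It then ranks the comparisons: "Primary comparisons will be between-groups comparisons of these variables at post-test". Two further comparisons follow: "We will also examine whether these variables differ overall by study group and whether changes in these variables differ by study group". No baseline covariate or baseline constraint is named, and the levels of time are not listed.

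Section 12.2 collects the purchase outcomes "each week of the 5-week shopping period, from receipts", and its additional details say that they "will be generated from each of the five weeks of receipt data using Nutritionist Pro software". By section 5.1 the first of these weeks is the baseline shop, made in person by everyone before randomisation. Three intervention weeks and one post-test week follow. Section 3.0 places the primary analyses both at post-test and across the whole study period.

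For intake, section 19.1 promises analyses parallel to those for purchases. The questionnaire that measures intake appears in section 12.3 as "Food frequency questionnaire (to be completed at post-test"), and sections 12.1 and 12.2 also place it only at post-test.

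**The concern.** Household purchases are likely to vary widely with household size and habits, and a household's own baseline week is an obvious predictor of its later weeks. Baseline receipts are a condition of randomisation, so every randomised participant should have them. A model with a separate mean for each group in each week makes no use of them in the contrast that is declared primary. In a trial with roughly 18 to 33 per arm, power is then lost without any saving, and a chance baseline difference carries into the estimate.

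Two smaller matters follow from the same sentences. An overall group effect averaged over every level of time would include a week in which randomisation guarantees an expected difference of zero. And a parallel of the longitudinal model has no time dimension when the questionnaire is given once.

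**Working it through.** **Inputs.** From section 19.2: d=0.96 and d=0.44, alpha 0.05, power 0.80, sample sizes of 15 and 54, and enrolment of up to 100. Assumed, because the documents do not say: two-sided testing, equal allocation, baseline to post-test correlation r of 0.3, 0.5 or 0.7, and, for averages over weeks, the same correlation between any two weeks. Arm sizes are 54/3 = 18 and 100/3 ≈ 33. The second is an upper bound, since section 19.2 says that the 100 allows for run-in losses and attrition.

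**The plan's own figures.** A two-sided two-sample t-test needs 19 per arm for d=0.96 and 83 per arm for d=0.44, which gives neither 15 nor 54. Both are reproduced as total sample sizes by a group-by-time interaction test in repeated-measures ANOVA with f=d/2, three groups, two time points, correlation 0.5 and λ = f²·N·m/(1−r):

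- d=0.96, N=15: λ = 0.48²×15×2/0.5 = 13.8, power 0.84.
- d=0.44, N=54: λ = 0.22²×54×2/0.5 = 10.5, power 0.81.

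These settings are inferred. If they are right, the sample size rests on a test of change, not on the post-test contrast that section 19.1 calls primary.

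**What the primary contrast estimates.** With a free mean for each group and week and complete data, the post-test contrast equals the raw difference in post-test means. In 150 simulated trials (18 per arm, five weeks, r=0.5, random-intercept model) the two differed by at most 8×10⁻¹⁵. The contrast's correlation with the chance baseline difference was 0.41, against −0.09 after baseline adjustment. The mean standard error was 0.331 unadjusted and 0.289 adjusted, as expected from √(2/18) = 0.333 and 0.333×√(1−0.5²) = 0.289.

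**Power of the post-test contrast, d=0.44.** Adjustment multiplies the variance by 1−r², so the effective d is 0.44/√(1−r²): 0.461, 0.508 and 0.616. A change score has variance factor 2(1−r), so its effective d is 0.44/√(2(1−r)): 0.372, 0.440 and 0.568. Two-sample noncentral t, ignoring the one degree of freedom spent on the covariate:

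| | r=0.3 | r=0.5 | r=0.7 |
|---|---|---|---|
| 33 per arm, unadjusted | 42% | 42% | 42% |
| 33 per arm, change score | 32% | 42% | 62% |
| 33 per arm, baseline-adjusted | 45% | 53% | 69% |
| 18 per arm, unadjusted | 25% | 25% | 25% |
| 18 per arm, baseline-adjusted | 27% | 32% | 44% |

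**Overall group effect, if baseline is one of five levels.** Let δ be the effect in each intervention week and c the share of it present at post-test. The five-week average is δ(3+c)/5 and the four-week post-randomisation average is δ(3+c)/4. Their ratio is 4/5 whatever c is. Variances of the averages at r=0.5:

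- five weeks: (1+4r)/5 = 0.600
- four weeks: (1+3r)/4 = 0.625
- four weeks, baseline-adjusted: 0.625−0.5² = 0.375

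Power with δ=0.44 and 33 per arm:

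| | Effect persists (c=1) | Effect stops (c=0) |
|---|---|---|
| Five weeks, baseline included | 44% | 28% |
| Four post-randomisation weeks | 61% | 39% |
| Four weeks, baseline-adjusted | 82% | 58% |

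**Intake.** One questionnaire per participant, at post-test, gives a group comparison at one time. Time, interaction and change terms cannot be estimated from it.

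**The case against.** The strongest reply is that the primary analysis is valid as written. The unadjusted contrast is unbiased under randomisation, and its standard error already allows for chance imbalance. Baseline is also not ignored: section 19.1 plans a comparison of changes, and hypothesis 1b in section 2.2 concerns increases in nutritional quality. All of that stands. What remains is that the change comparison is not primary, is less efficient than adjustment for every r below 1, and does no better than the raw contrast until r exceeds 0.5.

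The gain also depends wholly on an undocumented r. At r=0.3 it is about three percentage points, and at 18 per arm adjustment does not bring the trial near 80% power. That stands too.

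On the overall effect, the levels of time are not listed. Five weeks of receipts and the study-period wording of section 3.0 point strongly to baseline being included. If time covers only post-randomisation weeks, the dilution disappears. For spending, hypothesis 2 already names the intervention period as its window.

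Three stronger readings are tempting:

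- A reader might infer that the primary result is biased toward zero. It is not; the shrinkage concerns only the overall comparison.
- A reader might attribute the whole rise from 28% to 58%, or from 44% to 82%, to dilution. Dropping baseline alone gives 39% or 61%; the rest comes from adjustment.
- A reader might infer that intake cannot be analysed. A post-test group comparison can be run, and section 1.0 calls intake exploratory.

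**Conclusion.** The point holds as a loss of precision, not as a flaw in validity. As specified, the primary post-test contrast with complete data is the raw difference in means. At the upper-bound arm size, baseline adjustment would add about 3, 11 or 27 percentage points of power for d=0.44 at r of 0.3, 0.5 or 0.7. At 18 per arm it would add about 2, 7 or 19. Those gains rest on assumed correlations, equal allocation and two-sided testing.

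The four-fifths shrinkage of the overall effect is secondary. It applies to a non-primary comparison and depends on the well-supported but unstated reading that baseline is a level of time. The intake matter is a clarification of wording.

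**What to change.** In section 19.1:

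1. Estimate the primary post-test contrast from a constrained longitudinal model with a common baseline mean across arms. Alternatively, take the four post-randomisation weeks as outcomes, with the baseline value and its interaction with time as covariates. Use the matching baseline for the household-size and respondent-consumed versions.
2. List the levels of time, and define the overall group effect as the average over post-randomisation weeks only, keeping the intervention-period window that hypothesis 2 sets for spending.
3. State that the intake questionnaire is analysed as a single-time group comparison at post-test, with no time or change terms. The baseline purchase DASH score could serve as its covariate.

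The cost is analysis-plan wording; the baseline receipts are already required before randomisation. Settling it before the data are analysed also removes a later choice between adjusted and unadjusted results.

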## 5.0 Study Design\*

5.1 Describe and explain the study design (e.g. case-control, cross-sectional, ethnographic, experimental, interventional, longitudinal, observational).

Response:

This study has an experimental design. Participants will be randomly assigned to 1 of 2 interventions or a control group in which they will shop in-person as usual. Stratification factors will be sex and diabetes status: type 2 diabetic vs. at risk for type 2 diabetes, defined as a diagnosis of prediabetes or meeting criteria for increased risk of developing type 2 diabetes as determined by the American Diabetes Association Type 2 Diabetes Risk Test. In all groups, recipe cards that follow the evidence-based DASH diet and correspond to dietary recommendations for diabetic patients will be provided. The *Online* intervention will utilize online grocery shopping (shopping at a local grocery store via Instacart) to promote healthier purchasing, removing visceral factors that can lead to impulse purchases in stores. The *Defaults* intervention will augment this intervention, showing participants a default cart when they log into their accounts. They will be told that their cart has been filled with items that conform to a diet appropriate for diabetes prevention, management, and overall health and can be used to make the recipes from the provided recipe cards, and that they may modify it as they like.

At baseline, all participants will complete a survey online or via phone and then will grocery shop in-person as usual. Participants will then be randomized and receive further instructions. For the next 3 weeks, they will receive recipe cards and shop in accordance with their assigned study group. The following week (post), they will shop using the method of their choice (in-person, online) and complete a survey again. Household receipt data will be collected throughout the study. The baseline period will also serve as a run-in period, and participants who do not comply with study guidelines for baseline procedures (including guidelines for receipt submission) will not be randomized for further participation. Primary analyses will examine intervention effects on grocery purchases, with additional analyses on spending and dietary intake. All participant interactions will occur online or via phone.

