## **27.0 Compensation for Participation**

27.1 *Describe the amount and timing of any compensation to subjects, including monetary, course credit, or gift card compensation.*

Response:

All participants will receive up to \$75 for their participation in the study, with \$20 provided after completing baseline measures (\$20), \$10 after each intervention measure, and another \$25 provided after post-test. Participants will be paid as they complete study tasks using Clincard. Clincards will be provided after all screening procedures are completed, and eligibility (and interest in participating) has been determined. Payments during intervention weeks will also include reimbursements for typical costs of online shopping in Online and Defaults groups, given that these participants typically shop in-person but are being asked to shop online as part of the study. The typical cost of online shopping was estimated by applying Instacart service fees (5% of purchase) and data on average mark-ups on Wegmans items purchased via Instacart (~15% of purchase) to weekly grocery shopping amounts estimated using the USDA's official food plans (moderate-cost plan for a given family size:

<https://www.cnpp.usda.gov/sites/default/files/CostofFoodMar2019.pdf>). We also added the estimated cost of delivery (\$5.99) to the estimates. The payment to subsidize costs of online shopping will be calculated in this manner for each participant based on their family size. For example, for a 19-50-year-old single female participant, the USDA's moderate cost plan estimates \$59.60 in weekly food expenditures. Calculating the costs of online shopping indicated above (service fees, item mark-ups, and delivery) at this budget, we will provide an additional \$53.73 to this participant over the course of the study (\$17.91 per intervention week). For a family of two adults, this estimate changes to \$103.47 or \$34.49 per intervention week. As with other study payments, these payments will be provided to participants via Clincard provided they complete the study activities of the week.

☐ **N/A:** This study is not enrolling subjects, or is limited to records review procedures only. This section does not apply.

- ☐ **N/A:** There is no compensation for participation. This section does not apply.

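### The total-cart models leave out household size, a baseline variable the study already holds, so the primary post-test contrast is less precise than it could be

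*Combined protocol and SAP*

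**What the plan says.** Section 19.1 fits linear mixed models to calories, carbohydrates, sugar and nutritional quality of purchases "with study group, time, and their interaction as factors". Spending is analysed in parallel. No covariate is named. The same section states: "Primary comparisons will be between-groups comparisons of these variables at post-test".

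Household size appears once in the analysis plan: "We will conduct each analysis once for the total cart and then again examining these variables relative to household size". A further run covers items that the respondent will consume. The plan does not say which of these versions is decisive.

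The outcome is measured on the household. Section 5.1 says: "Household receipt data will be collected throughout the study". Section 12.2 lists the purchase variables for "each week of the 5-week shopping period, from receipts".

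The size of each household must be known. The household-relative analysis needs it, and so does the subsidy in section 27.1: "The payment to subsidize costs of online shopping will be calculated in this manner for each participant based on their family size". The questionnaire is an attachment that is not shown, so its recording is inferred from these two uses.

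Household size is not a stratification factor. Sections 1.0 and 5.1 name sex and diabetes status, and section 12.1 names diabetes status only.

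**The concern.** A household of four buys more than a household of one, whatever the study arm. In a comparison of total carts at one time point, that difference is noise unless the model accounts for it. Neither the stratification nor the total-cart model does so. A reader might expect the mixed model to deal with it through repeated measures on the same household, but a between-group contrast at a single week is not a within-household comparison.

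What is at stake is the width of the confidence intervals and the influence of a chance imbalance in household size. Enrolment is capped at 100 over three arms, so there is little precision to spare for the smaller effect in section 19.2.

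**Working it through.** **1. The plan's own sample sizes.** Section 19.2 gives 15 participants for d = 0.96 and 54 for d = 0.44, with alpha 0.05 and power 0.80. Both can be reproduced as total numbers for a group-by-time interaction F test with f = d/2, three groups, two time points and correlation 0.5. These settings are inferred, not stated. The noncentrality is λ = f² × N × 2 / (1 − 0.5).

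- d = 0.96: λ = 0.48² × 15 × 4 = 13.82, df 2 and 12, power 0.840.
- d = 0.44: λ = 0.22² × 54 × 4 = 10.45, df 2 and 51, power 0.809.

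An interaction test of this kind cancels stable household differences. The post-test contrast named as primary in section 19.1 does not.

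**2. The protocol's own figures on household size and spending.** Section 27.1 takes 5% + 15% = 20% of weekly spending plus $5.99. For a single woman, 0.20 × 59.60 + 5.99 = $17.91, as stated. The two-adult payment of $34.49 implies (34.49 − 5.99) / 0.20 = $142.50 a week, and 142.50 / 59.60 is about 2.4. These are budget-plan amounts, not receipts, but they show that household size is expected to drive purchases strongly.

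**3. Does the planned mixed model remove the variance?** A simulation used a random intercept, five weeks and 33 per arm (100 / 3, the ceiling if allocation is equal and everyone enrolled is randomised). The standard error of the post-test contrast was 0.245 to 0.249 SD. A plain two-group difference gives √(2/33) = 0.246 SD. The random intercept therefore removes none of it. Let R² be the share of post-test variance explained by household size. Adding household size cut the variance of the contrast to 0.90, 0.69 and 0.49 of its value for R² = 0.1, 0.3 and 0.5.

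**4. How large might R² be?** Assume that cart = size × household factor × weekly factor, with factor means of 1 and CVs of 0.3 and 0.3, and that household size has mean 2.4 and SD 1.27. None of these values is in the documents.

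- E[size²] = 2.4² + 1.27² = 7.373
- Total variance = 7.373 × 1.09 × 1.09 − 5.76 = 3.000
- R² = 1.613 / 3.000 = 0.54
- Covariance of baseline and post-test weeks = 7.373 × 1.09 − 5.76 = 2.277
- Residual variance, baseline week only = 3.000 − 2.277² / 3.000 = 1.272
- Residual variance, baseline week and size = 1.387 − 0.664² / 1.387 = 1.069, where 1.387 = 3.000 − 1.613 and 0.664 = 2.277 − 1.613
- Ratio = 1.069 / 1.272 = 0.84, a cut of 16%

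Over exponents 0.8 to 1.0, between-household CV 0.3 to 0.4, weekly CV 0.3 to 0.6 and two assumed size distributions, R² was 0.19 to 0.54. The cut beyond the baseline week was 8% to 18%. That is worth 1/0.92 − 1 = 9% to 1/0.82 − 1 = 22% more participants.

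**5. Power for the post-test contrast.** With d = 0.44, two-sided alpha 0.05, 33 per arm and a normal approximation, power = Φ(0.44 / √((1 − R²) × 2/33) − 1.96).

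| R² | Power | n per arm for 80% |
|---|---|---|
| 0 | 43.1% | 82 |
| 0.1 | 47.0% | 73 |
| 0.2 | 51.5% | 65 |
| 0.3 | 57.0% | 57 |
| 0.5 | 71.5% | 41 |

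These gains assume no baseline adjustment, as the plan stands. Adjusting for the baseline week alone lifts power from 42% to 53-69% (t test, correlation between weeks 0.5 to 0.7). Household size then adds about 1 to 6 percentage points for R² of 0.1 to 0.3.

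**6. Chance imbalance.** With the same assumed SD, the between-arm difference in mean household size has a standard error of 1.27 × √(2/33) = 0.31 persons, which is 13% of the mean of 2.4.

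**The case against.** The plan does not ignore household size. The household-relative run removes much of the same variance with the same data. Under the assumptions in step 4 it is the more precise of the two. Its residual variance relative to the squared mean is 1.09² − 1 = 0.188, against 1.387 / 5.76 = 0.241 for the total cart with a linear size covariate. It was more precise in all 16 scenarios simulated, by 6-22%. This stands. It rests on an intervention effect proportional to size, and the rescaled outcome answers a different question, so it does not make the total-cart analysis efficient. It does mean that there is no case for demoting the household-relative version.

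A reader might infer that the unadjusted contrast is biased. The documents do not support that: assignment is randomised, so the contrast remains valid.

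Nor does the point threaten the main planned effect. At d = 0.96 and 33 per arm, power is already 97.4%, and the gain is negligible.

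Baseline adjustment would do more than household size. That is true under the assumptions used, but section 19.1 specifies neither. The separate analysis of change cancels stable additive household differences, but it is not the primary comparison. Section 8.4 describes the study as a pilot, which lowers the stakes without removing the gain.

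**Conclusion.** The point holds as a loss of precision and as exposure to chance imbalance in the total-cart models for calories, carbohydrates, sugar and dollars. It is not a validity error. It need not extend to DASH scores, which are meant to measure quality rather than quantity.

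Its size rests on assumptions, because the documents give no distribution of household size, no scaling exponent and no CV. Under the ranges used, household size explains about 19-54% of post-test variance alone and cuts residual variance by about 8-18% beyond the baseline week. It matters most for the smaller effect of d = 0.44 and hardly at all for d = 0.96. The adjustment is worth making because it is nearly free.

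**What to change.** In section 19.1, prespecify household size as a covariate in the total-cart models for calories, carbohydrates, sugar and dollars. Include its interaction with time, so that the post-test contrast is adjusted with the post-test slope.

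If baseline is also adjusted for, say how. The baseline week is one of the five outcome weeks, so it cannot simply be added as a covariate as well. Either remove that week from the outcome rows, or keep it and constrain the baseline group means to be equal.

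Leave the household-relative analysis as planned, without demoting it.

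The cost is a few degrees of freedom (one for household size plus four for its interaction with five weeks, if it enters linearly) and slightly more analysis wording. No new data are needed.
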